At the end of the study, all participants will return the supply of Amara. The study team will assess compliance by counting the empty bottles and weighing partly used bottles. Patients will be asked whether they wish to continue the medication (yes / no). If the response is positive, then ongoing treatment will be recommended. Amara is classified by Swissmedic as dispensing category D available following discussion with specialist without prescription ("Abgabekategorie D: «Abgabe nach Fachgespräch»).

Overall, approximately 30 minutes will be needed to complete the questionnaires on each occasion. The total time required per patient during the study is a maximum of 8 hours (reading documents, filling in questionnaires, gastric emptying study (twice)).

During the period the participants are enrolled in this study no additional outpatient examinations are planned. If, while someone is participating in the study, acute symptom occur and the need arises for early outpatient assessment or inpatient admission to the clinic, the study would be terminated for this subject as of this date.

Limitations:

- The study will provide a prospective assessment of perceived treatment effectiveness; however, a large non-specific (placebo) effect is likely to be present as in any open-label, single-arm study in patients with functional gastrointestinal disease. This limitation is factored into the power calculation which requires at least a moderate treatment effect for Amara to be considered effective. Note that the secondary analysis that will identify baseline factors (e.g., age, sex, symptom severity, gastric emptying rate) that associate with treatment effect will be relatively less sensitive to this confounding factor.

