7.1 Eligibility criteria

Participants fulfilling all of the following inclusion criteria are eligible for the study:

- Patients referred by their treating physician to the Center for integrative Gastroenterology at the Clinic Arlesheim
- Age over 18 years and \leq 75 years of age
- Patients with diagnostic criteria of Functional Dyspepsia with Postprandial Distress (Rome IV criteria) with Leuven Dyspepsia Score "at least moderate" severity (≥2/4) on at least two subscales (≥4 total). Normal endoscopy in previous 3 years.
- Signed informed consent
- No change in medical treatment (e.g., proton pump inhibitor, antidepressants) during the last one month or for the duration of the period
- No planned introduction or dose increases of (conventional) anxiolytics or antidepressants during the last one month or for the duration of the period
- Good German knowledge (at least level B2 from Common European Framework of Reference for Languages)

The presence of any one of the following exclusion criteria will lead to exclusion of the participant:

- Acute life-threatening conditions
- Withdrawal of informed consent
- Clinically relevant psychiatric comorbidity (HADS score >11 for anxiety or depression)
- Advanced liver (Child score > 6) or kidney disease (GFR < 60)
- History of major gastrointestinal surgery (appendectomy, hysterectomy, cholecystectomy, hernia repair are not exclusion criteria)
- Allergy to any component of Amara
- Treatment with Amara during the last one month prior to the study
- Pregnancy and lactation

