7.4 Criteria for withdrawal / discontinuation of participants

In emergency situations, where acute symptoms develop or side effects are suspected to be associated with the Amara intake, treatment can be discontinued. The participation can also be terminated by the PI, by the Clinic Arlesheim or by the manufacturer of Amara if there is a suspicion of damage to health caused by the drug or a product defect, respectively. Also, as mentioned before, if there are any signs of patients unwilling to participate in the study it will result in the participant being excluded from the study.

If a participant does no longer fulfil the eligibility criteria at some point of the study, it will lead to the discontinuation of this participant from the study.

Participant recruitment will continue until 60 patients have completed the treatment arm of the study.

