9.2.5 Assessments in participants who prematurely stop the study

Assessments in participants who are withdrawn from the study prematurely, depend on the type and severity of the SAE. Participants who are withdrawn from the study prematurely due to the occurrence of exclusion criteria other than SAEs will not require any follow-up.

See chapter 10. for further information about follow-ups for participants who prematurely stop the study.

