10.1.2 Reporting of serious adverse events (SAE) and other safety related events

As stated in the contract between the Clinic Arlesheim and Weleda AG, we will comply with our pharmacovigilance obligations. UAWs, SAEs and SUSARs will be reported to Weleda AG (see contact below) within a maximum of 24 hours. Any other side effects which are collected through the questionnaires will be notified to Weleda AG as soon as possible.

Address: WELEDA AG, [name]

Contact: [name], [contact], [contact]

Reporting of SAEs:

All SAEs must be reported immediately and within a maximum of $\underline{24 \text{ hours}}$ to the PI of the study. The PI will re-evaluate the SAE and make a causality assessment of the event to the study drug.

SAEs resulting in death are reported to the Ethics Committee via BASEC within 7 days.

If the possibility arises that a patient can admit the Clinic Arlesheim earlier than expected, it will lead to the discontinuation of this participant from the study. This hospital stay will not be considered as an SAE. Additionally, if a SAE is a clear result of the underlying disease, this SAE is exempted from expedited reporting.

Reporting of SUSARs

The Sponsor-Investigator needs to report SUSARs to the Ethics Committee via BASEC within 7 days, if the event is fatal, or within 15 days (all other events).

Reporting of Safety Signals

All suspected new risks and relevant new aspects of known adverse reactions that require safetyrelated measures, i.e. so called safety signals, must be reported to the Sponsor-Investigator within 24 hours. The Sponsor-Investigator must report the safety signals within 7 days to the Ethics Committee via BASEC.

Reporting and Handling of Pregnancies

Pregnant participants will be excluded from the clinical study

Periodic reporting of safety

An annual safety report is submitted once a year to the local Ethics Committee via PI.

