11.4.2 Primary Analysis

In the intention to treat analysis, all patients who have completed study questionnaires at baseline and after four-weeks of treatment will be included. Following covariates will be included in multivariate models: age, gender, dyspepsia symptom severity (LDQ), other gastrointestinal symptoms, psychological state and gastric function (sensitivity, emptying) at baseline.

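### Section 6.1 ends study participation when acute symptoms need an early visit, with no LDQ required, so patients with a dyspeptic flare on Amara can drop out of the primary comparison and be replaced; this favours improvement by an unknown, possibly negligible, amount

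*Protocol*

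**What the plan says.** Section 6.1 deals with acute symptoms during participation: if they occur and "the need arises for early outpatient assessment or inpatient admission to the clinic, the study would be terminated for this subject", with effect from that date.

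What is collected afterwards is set out in two places. Section 8.5 keeps the data gathered up to withdrawal. Section 9.2.5 says: "Assessments in participants who are withdrawn from the study prematurely, depend on the type and severity of the SAE". It adds that withdrawals for exclusion criteria other than SAEs need no follow-up. Neither section mentions the LDQ.

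The primary outcome (Sections 4.2 and 5.1) is the change in LDQ from visit 1 to visit 3, and the study schedule places the LDQ at those two visits. Section 11.4.2, under the label of intention to treat, defines the primary set thus: "all patients who have completed study questionnaires at baseline and after four-weeks of treatment will be included". Section 11.5 classes anyone with only the screening or baseline questionnaire as a dropout to be replaced. Section 7.4 states: "Participant recruitment will continue until 60 patients have completed the treatment arm of the study".

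Two further texts are relevant. Section 7.1 lists as an inclusion criterion "No change in medical treatment (e.g., proton pump inhibitor, antidepressants) during the last one month or for the duration of the period", and Section 7.4 provides that a participant who "does no longer fulfil the eligibility criteria at some point of the study, it will lead to the discontinuation of this participant". Section 10.1.2 covers the possibility that "a patient can admit the Clinic Arlesheim earlier than expected, it will lead to the discontinuation of this participant from the study", followed by "This hospital stay will not be considered as an SAE".

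**The concern.** The participants have functional dyspepsia and are under the care of the gastroenterology clinic that runs the study. A flare of dyspepsia is a natural reason for an early visit. For such a patient, leaving the study depends on the same symptoms that the LDQ measures. If the final LDQ is then never taken, the patient is absent from the primary comparison and the place goes to someone who completes.

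The remaining patients will tend to have better changes than all patients who started treatment. There is no comparator arm in which the same selection could occur and partly cancel. Section 11.1 intends the effect size found here to feed the sample size of a later confirmatory study. The limitations in Section 6.1 discuss placebo response, reliance on reported intake, other treatments and the short duration, but not this selection.

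The point is confined to dyspeptic flares during Amara treatment. For events in the run-in and for acute symptoms unrelated to dyspepsia, no direction of bias follows.

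**Working it through.** **The chain in the text.**
1. Trigger: acute symptoms needing early assessment or admission end the study for that patient (6.1).
2. No outcome is required afterwards (8.5, 9.2.5). None is forbidden either.
3. Without the four-week questionnaire the patient is outside the primary set (11.4.2).
4. The patient is a dropout and is replaced (11.5), until 60 have completed (7.4).
5. If the early visit leads to a new or changed medicine, the inclusion criterion on stable treatment is probably lost, and 7.4 then discontinues the patient as well. This route is conditional and adds little to step 1.

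**Inputs for the size.** The protocol gives no rate of early visits, so there is no figure of its own to reproduce. The yardstick is the planned effect of 0.4 (Section 11.2), read here as 0.4 SD of the change. Everything else is assumed:
- p: fraction of treated patients removed under the rule while on Amara (2%, 5%, 10%);
- d: share of those removed for a dyspeptic flare (0.5 or 1), other removals being neutral;
- g: how much worse the flare patients' change is than the completers', in SD. With completers improving by 0.4, g = 0.4 means no change and g = 1 means worsening by 0.6 SD.

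**Formula.** Mean improvement in all treated = completers' improvement − p × d × g, so the inflation is p × d × g. In SD, with the share of 0.4 in brackets:

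| p | d | g = 0.4 | g = 1 |
|---|---|---|---|
| 2% | 0.5 | 0.004 (1%) | 0.010 (2.5%) |
| 2% | 1 | 0.008 (2%) | 0.020 (5%) |
| 5% | 0.5 | 0.010 (2.5%) | 0.025 (6.25%) |
| 5% | 1 | 0.020 (5%) | 0.050 (12.5%) |
| 10% | 0.5 | 0.020 (5%) | 0.050 (12.5%) |
| 10% | 1 | 0.040 (10%) | 0.100 (25%) |

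Over the 5% and 10% rows, a reported 0.40 SD would correspond to 0.40 − 0.01 = 0.39 down to 0.40 − 0.10 = 0.30 SD among all treated.

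**Patients replaced** to reach 60 completers: 60/(1 − p) − 60 = 1.2, 3.2 and 6.7 at 2%, 5% and 10%.

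**Outer bound.** Suppose there is no true change, changes are normally distributed, and the rule removes exactly the worst fraction f. The completers' mean change is then −φ(c)/(1 − f), with c the 1 − f quantile of the standard normal: −0.049, −0.109 and −0.195 SD at f = 2%, 5% and 10%. Simulating 20,000 trials of 60 completers, the chance of a significant improvement at two-sided 5% is about 5%, 14% and 41%, against a nominal 2.5%. These figures imply g of 0.049/0.02 = 2.45, 0.109/0.05 = 2.2 and 0.195/0.10 = 1.95, about twice the largest value in the table or more. They bound the problem and do not estimate it.

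**The case against.** The strongest case against is that the trigger is narrow and its frequency unknown. It needs acute symptoms and a need for early assessment within about four weeks, in patients with a normal endoscopy, and only the dyspeptic events count here. At 2% removed the effect is negligible, and the 25% figure needs every assumption at its extreme. This stands, and it limits the point to a modest one.

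Second, loss of the LDQ is not inevitable. The schedule allows visit 3 at 28±14 days, so an early visit from about day 14 could fall inside the window, and Section 9.3.2 lets questionnaires be completed in the clinic. Daily symptom entries up to termination also survive. This stands in part: nothing tells the site to treat the early visit as visit 3, Section 9.3.2 books that visit at 4 to 6 weeks, and the primary comparison does not use the diary.

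Third, a reader might take Section 10.1.2 as a second symptom-driven removal rule whose admissions are kept out of the SAE count. The text does not support that firmly. It names neither acute symptoms nor worsening, and it may describe a planned stay brought forward, which would explain why it is not an SAE. It is possible support only. Nor does the treatment stop for acute symptoms in Section 7.4 conflict with 6.1; the two differ in scope.

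Fourth, a reader might infer that the selection could carry the trial over its requirement that at least 60% improve. If 36 of 60 completers improved, counting 1, 3 or 7 removed patients as failures gives 36/61 = 59.0%, 36/63 = 57.1% or 36/67 = 53.7%. But the 60% is rationale for the sample size in Section 11.2. The planned test is of LDQ change against no change (11.1, 11.4), so no decision rule is crossed.

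Fifth, Section 6.1 itself says the design cannot evaluate efficacy, and a large placebo response is expected. That tempers the consequence, but it neither discloses nor corrects outcome-dependent removal. The completer-only set also affects other dropouts. This route differs in that the protocol itself imposes the removal.

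**Conclusion.** The point holds for dyspeptic flares during Amara treatment. As written, the plan ends participation for these patients, requires no further LDQ, leaves those without one out of the primary set and replaces them. The direction, towards improvement, follows if flare patients would have had worse final scores than completers, which is likely but assumed.

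The size cannot be established from the protocol. It is 0.004 to 0.02 SD at 2% removed, and 0.01 to 0.10 SD over 5% to 10% removed, with the upper end a worst case. The documents do not show that a significant result would be false, that the primary conclusion would change, or that an LDQ is barred after termination. The change is worth making because it is cheap and because no later analysis plan can recover questionnaires that were never collected.

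**What to change.** Amend Sections 6.1 and 9.2.5, and 7.4 and 10.1.2 for consistency, so that an early visit, an admission or a resulting change of medication may stop Amara but does not end outcome collection. At the early visit take the LDQ before any rescue treatment, and record the date, the reason and any rescue given. Still send the visit 3 questionnaire link on the scheduled day.

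In Sections 11.4.2 and 11.5, keep these treated patients in the primary comparison and do not class them as replaceable dropouts. Use the pre-rescue early-visit LDQ where rescue treatment was given. Otherwise use the visit 3 LDQ, or the early-visit LDQ if visit 3 is missing. Making the visit 3 score primary even after rescue would credit the rescue benefit to Amara and bring back a bias in the same direction. Report that version, and a count treating these patients as not improved, as sensitivity analyses. Stopping Amara for safety or pregnancy is unaffected.

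Cost: one amendment and one three-question LDQ per event; the e-mailed link already exists. Downside: a few scores will be taken early, at a symptom peak or off drug.

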Study Product / Intervention:	In this study the test medication (Amara drops) will be taken by the participants before meals. The herbal preparation is manufactured by Weleda AG, Arlesheim. Besides the bitter substances Artemisia absinthium, Cichorium intybus, Juniperus and Gentiana lutea, Amara Drops contain also Centaurium, Peucedanum, Achillea millefolia, Salvia officinalis and Taraxacum, all suspended in an alcohol-based tincture. The full indication text licensed by Swissmedic is: "According to the anthroposophical knowledge of man and nature, Weleda Amara-Drops can be used for digestive complaints such as heartburn, flatulence and bloating after meals, to stimulate the bile flow and for loss of appetite and nausea. The effect of Weleda Amara drops is based on a balanced mixture of medicinal plants with tonic (invigorating) and aromatic bitter substances, which are suitable for stimulating digestion. Weleda Amara drops mildly stimulate the secretion of saliva and gastric juices, promote the formation and secretion of bile and thus facilitate the digestion of fats. In addition, they are effective against flatulence and cramps."
Control Intervention:	No control group
Number of Participants with	Participants: 60 patients with functional dyspepsia with postprandial distress (Rome IV criteria).
Rationale:	There are no previous studies that have assessed the effect of Amara Drops in functional dyspepsia. Before randomized double blind controlled studies can be considered it is appropriate to assess perceived changes in symptom burden and physiological effects of Amara in clinical practice. At the same time the feasibility of recruiting this patient group and performing gastric emptying and other studies will be assessed. In this prospective open label study, placebo effects are likely to be present. Previous randomized controlled trials indicate that this can be up to 40%. To demonstrate convincing evidence of clinical efficacy a minimum 60% response rate above no treatment (run-in phase) must be demonstrated. Based on these considerations, for the primary outcome, power calculation suggests that at least 58 patients are required to detect moderate effects on perceived symptom burden at a convincing level of statistical significance (beta 0.9, alpha <0.01).
Study Duration:	2 years

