Study Schedule:	Month Year of First-Participant-In (planned): July 2022 Month Year of Last-Participant-In (planned): August 2024 Month Year of Last-Participant-Out (planned): September 2024
Investigator:	[name]. med. [name]
investigator.	Leitender Arzt, Zentrum für Integrative Gastroenterologie
	Leiter, Magen Darm Funktion: Basel, Labor und Klinik für funktionelle Magendarm Erkrankungen und Motilitätsstörungen
	[contact]
	[contact]
Study Centre:	Single Centre, Clinic Arlesheim (CLA), [name]

Statistical Considerations:	Differences between the scores from the primary and secondary outcome measurement variables – at baseline (following run-in) and after either 4- weeks treatment - will be compared initially by t-test if the data is normally distributed and Wilcoxon rank sum test when data are not normally distributed. In addition, we will perform univariate and multivariate linear regression analysis in which potential covariates will be considered; confounding will be evaluated by adding these variables to the linear regression model and looking at the change of the regression coefficients. These variables will include participants' gender, age, perceived symptom severity and gastric function at baseline.
	In the analysis of the primary outcome two-tailed $p \le 0.05$ will be considered statistically significant. Since the evaluation of the secondary endpoints is purely exploratory, other p-values will be calculated but reported without claiming significance,
GCP Statement:	This study will be conducted in compliance with the protocol, the current version of the Declaration of Helsinki, the ICH-GCP as well as all national legal and regulatory requirements.

ABBREVIATIONS

13C BT	¹³ C Acetate Breath Test
AE	Adverse Event
BASEC	Business Administration System for Ethical Committees, (https://submissions.swissethics.ch/en/)
CA	Competent Authority (e.g. Swissmedic)
CEC	Competent Ethics Committee
ClinO	Ordinance on Clinical Trials in Human Research (in German: KlinV)
CRF	Case Report Form
CTCAE	Common terminology criteria for adverse events
DSUR	Development safety update report
eCRF	Electronic Case Report Form
EKNZ	Ethikkommission Nordwest- und Zentralschweiz
HADS	Hospital Anxiety and Depression Scale
GCP	Good Clinical Practice
HRA	Federal Act on Research involving Human Beings (in German: HFG)
HRV	Heart Rate Variability
IB	Investigator's Brochure
IBS-SSS	Irritable Bowel Syndome Symptom Severity Score
ICS	Internal Coherence Scale

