3.8 Justification of choice of study population

Study participants will be recruited from patients referred to Gastroenterologists at Clinic Arlesheim for

assessment of dyspeptic symptoms. Investigations in this patient group identify an organic cause of these persistent symptoms in less than 1 in 4 cases.(16) Instead, functional dyspepsia is considered to be a disorder of brain-gut interaction, with symptoms related to both abnormal gastric motor function (e.g. delayed gastric emptying) and sensory function (peripheral hypersensitivity but also abnormal central processing).(1) Conservative measures (e.g. reduction in dietary fat) and medical treatment (e.g. acid suppression, prokinetics) often fail to improve symptoms.(5) Moreover, concerns about long-term side effects for certain medications (e.g. domperidone, metoclopramide),(20) and high rates of intolerance to prescription medications are reported.(5, 9) For these reasons, there is a clinical need for new and effective treatments of functional dyspepsia. Complementary and alternative medicines (CAM) based on natural products, such as plant-based "phytotherapy", are particularly appealing.(7, 9)

There are no previous studies that have assessed the effect of Amara Drops in functional dyspepsia. Before randomized double blind controlled studies can be considered prospective, open-label therapeutic study to assess perceived changes in symptom burden will be performed (at the same time the feasibility of recruiting this patient group and performing gastric emptying and other studies will be assessed). In this prospective open label study, placebo effects are likely to be present. Previous randomized controlled trials of therapy in functional gastrointestinal disorders indicate that this can be up to 40% in this group.(15) To compensate for this confounding factor and to demonstrate convincing changes in perceived symptom burden at least 60% of patients should show improvement on-treatment compared to off-treatment (run-in phase). Assuming a moderate effect (Cohen's effect size of 0.4) on the primary outcome measure (effect size and standard deviation as in a previous paper by Carbone et al. (21)) power calculation suggests that 58 patients are required to detect a significant effect at a convincing level of statistical significance (beta 0.9, alpha <0.01).

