11. STATISTICAL METHODS

11.1 Hypothesis

Null hypothesis: There will be no difference in the primary outcome (LDQ score) between baseline and after four weeks of Amara treatment.

Alternative hypothesis: The LDQ score after four weeks treatment is different from the LDQ-score before the treatment.

In the case of statistical significance, the null hypothesis is rejected and the described difference (reduction or increase) is found to be proven according to the alternative hypothesis.

All secondary outcomes are purely exploratory, where effects are looked at and no Null Hypothesis is tested. This study is designed to get an idea of the effect size, since an estimation of the effect size is needed in order to calculate the sample size of a subsequent confirmatory study.

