11.2 Determination of Sample Size

In this prospective open label study, placebo effects are likely to be present. Previous randomized controlled trials of therapy in functional gastrointestinal disorders indicate that this can be present in up to 40% of patients.(15) To compensate for this confounding factor and to demonstrate convincing

changes in perceived symptom burden at least 60% of patients should show improvement on-treatment compared to off-treatment (run-in phase). Assuming a moderate effect (Cohen's effect size of 0.4) on the primary outcome measure (effect size and standard deviation as in a previous paper by Carbone et al. (21)) power calculation suggests that 58 patients are required to detect a significant effect at a convincing level of statistical significance (beta 0.9, alpha <0.05). In the context of this study, the inclusion of 60 patients should also be sufficient to inform the design of any, future randomized, placebo-controlled study.

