11.4 Planned Analyses

The statistic evaluation will be performed with SPSS (IBM SPSS Statistics, NY: IBM Corp.), version 26 or higher or Graphpad Prism (MacKiev Software), version 9.3.1 or higher or higher for PC or Mac. The demographic data will be analysed with descriptive statistics as average ± standard deviation (SD) for continuous variables and with percentage of total (%) for categorical variables.

Differences between the scores from the primary and secondary endpoint variables – at baseline and after 4-weeks treatment - will be compared initially by t-test if the data is normally distributed and Wilcoxon rank sum test when data are not normally distributed. In addition, if data is normally distributed we will perform univariate and multivariate linear regression analysis in which potential covariates will be considered; confounding will be evaluated by adding these variables to the linear regression model and looking at the change of the regression coefficients. These variables will include participants age, gender, symptom severity, psychological state and gastric function (sensitivity, emptying) at baseline.

In the analysis of the primary outcome two-tailed $p \le 0.05$ will be considered statistically significant. Since the evaluation of the secondary endpoints is purely exploratory, other p-values will be calculated but reported without claiming significance,

Data will be transferred from the REDCap software to the statistics program Prism for evaluation, where data are password protected and only accessible to the persons involved in the study.

All analyses will be performed at Klinik Arlesheim by the research group of [name]. [name], Department of Gastroenterology, Klinik Arlesheim.

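### Section 6.1 says the placebo effect is built into the power calculation and a moderate effect is required; the calculation shown has no placebo term and the test requires neither

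*Protocol*

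**What the plan says.** Section 6.1 (Limitations) expects a large non-specific effect and then says: "This limitation is factored into the power calculation which requires at least a moderate treatment effect for Amara to be considered effective".

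The relevant parts of the plan are these:

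- **Sample size (sections 3.8 and 11.2).** 58 patients, a moderate Cohen's effect size of 0.4 on the primary outcome, with "effect size and standard deviation as in a previous paper", and a value of 0.9 labelled beta. Alpha is below 0.05 in section 11.2 and below 0.01 in section 3.8 and the synopsis.
- **Null hypothesis (section 11.1).** "There will be no difference in the primary outcome (LDQ score) between baseline and after four weeks of Amara treatment". It is rejected on statistical significance.
- **Decision rule (section 11.4 and synopsis).** "In the analysis of the primary outcome two-tailed" p at or below 0.05 counts as significant.
- **Placebo compensation.** Placebo response is put at up to 40%. Section 3.8 continues: "To compensate for this confounding factor and to demonstrate convincing changes in perceived symptom burden at least 60% of patients should show improvement", and section 11.2 says the same. The synopsis (Number of Participants with Rationale) says that "a minimum 60% response rate above no treatment (run-in phase) must be demonstrated".
- **Baseline.** The primary outcome runs from visit 1 to visit 3 (sections 4.2 and 5.1). The 60% criterion is measured against the run-in, and the synopsis places the comparison "at baseline (following run-in) and after either" 4 weeks of treatment.
- **Interpretation.** Section 5.1 says placebo and treatment effects are added together, yet also makes the LDQ the result that verifies efficacy. Section 6.1 says the design cannot evaluate efficacy.

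**The concern.** The section 6.1 sentence makes two factual claims about the protocol's own calculation: that placebo response is accounted for in it, and that a moderate effect is a condition of success. If neither can be found in the stated inputs, null hypothesis or decision rule, a reader may take a significant result as already discounted for placebo when it is not. A single-arm test against zero change can be significant on non-specific improvement alone. The only safeguard named is the 60% criterion. The synopsis says it must be demonstrated, but nothing in section 11 would show whether it was met.

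**Working it through.** **1. The protocol's own figure.** Inputs: effect size d = 0.4, power 0.90 (reading the stated beta of 0.9 as power), alpha 0.05 (section 11.2). For a mean change tested against zero, n = ((z_alpha + z_power)/d)².

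- One-sided 0.05: ((1.645 + 1.282)/0.4)² = 53.5, so 54. The t-test gives 55. A Wilcoxon allowance gives 55/0.955 = 57.6, so 58.
- Two-sided 0.05: ((1.960 + 1.282)/0.4)² = 65.7, so 66. The t-test gives 68, Wilcoxon 72.
- Two-sided 0.01: 93, 97 and 102 respectively.

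So 58 can be reached from the stated inputs, though only in the one-sided Wilcoxon variant. No placebo rate or placebo shift enters the formula.

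**2. Does the test require a moderate effect?** Inputs: n = 60 completers (section 7.4), two-tailed 0.05 (section 11.4), and a paired t-test on the change (assumed, since section 11.2 names no test). The smallest significant observed effect is t(0.975, 59)/√60 = 2.001/7.746 = 0.258 in units of the SD of change. The protocol does not say which SD its 0.4 refers to, so the raw-score version is also shown, multiplying by √(2(1 − r)) for pre-post correlation r:

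| Alpha (two-sided) | SD-of-change units | Raw, r = 0 | Raw, r = 0.2 | Raw, r = 0.5 | Raw, r = 0.7 |
|---|---|---|---|---|---|
| 0.05 | 0.26 | 0.37 | 0.33 | 0.26 | 0.20 |

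At 0.05 every value is below 0.4. At the 0.01 of section 3.8 and the synopsis, the threshold is 2.662/7.746 = 0.344 SD of change. In raw units it is 0.43 at r = 0.2, and it reaches 0.4 at r = 0.32.

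**3. What could a non-specific change alone do?** The documents give no placebo shift on the LDQ, so the shift is an assumption. Probability of significance at n = 60, two-sided 0.05 (noncentral t):

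| Assumed non-specific shift | 0.2 | 0.3 | 0.4 | 0.5 |
|---|---|---|---|---|
| SD-of-change units (same as raw, r = 0.5) | 33% | 63% | 86% | 97% |
| Raw units, r = 0.2 | 23% | 44% | 67% | 85% |
| Raw units, r = 0.7 | 50% | 84% | 98% | over 99% |

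This is power to detect a real pre-post change, not type I error.

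**4. Where is the 60% criterion used?** It appears in the synopsis and sections 3.8 and 11.2. It is absent from the hypotheses (11.1) and from the planned, primary and secondary analyses (11.4, 11.4.2, 11.4.3). Improvement on the LDQ is not defined. The reduction of more than 60% in section 5.1 is an expected fall in mean score, a different quantity.

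**5. Could a responder calculation lie behind 58?** Cohen's h for 60% versus 40% is 2(arcsin√0.6 − arcsin√0.4) = 0.403. An exact one-sided binomial test at 0.05 with n = 58 rejects a 40% rate at 30 or more responders (actual level 0.047), with power 0.921 at a true 60%; from n = 58 upward, power stays at 90% or more. So this route also gives 58. At two-sided 0.05 it needs 68, or 72 for power that stays at 90% or more.

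**The case against.** The strongest counter-argument is step 5. The protocol says Cohen's effect size without saying d, the two rates named just before it give h = 0.403, and an exact one-sided test of them gives 58. A reader might infer from the stated inputs that the sample size certainly ignores placebo response. The documents do not support that: a calculation with a 40% null cannot be excluded. What they do support is that no placebo term is shown or carried into the test. The text ties the 0.4 to the effect size and SD of a cited questionnaire paper, no responder test is planned, and that route is one-sided while the analysis is two-tailed.

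Second, at alpha 0.01, in raw-score units and with a correlation below about 0.32, an observed effect above 0.4 would be needed. That is correct, but the stated analysis rule is 0.05; the two alphas are a separate conflict.

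Third, much of the consequence is disclosed. Section 6.1 expects a large placebo effect, section 5.1 says the effects are summed, section 6.1 says efficacy cannot be evaluated, and section 11.1 describes the aim as getting an idea of the effect size. It would be wrong to infer that the protocol hides the problem. The disclosures are, however, what the section 6.1 sentence conflicts with.

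Fourth, a responder definition is often left to a separate analysis plan. Section 6.2.3 says the analysis plan is in the protocol, which weakens this defence. In any case, a later document could not make the section 6.1 sentence true of the calculation shown. Finally, the two wordings of the 60% criterion may be meant as the same idea, so they are untidy rather than clearly contradictory.

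**Conclusion.** The point holds in this form: as shown, the power calculation has no placebo term, the null is zero change, and a moderate effect is not a condition of success. With 60 completers, significance at two-tailed 0.05 begins at 0.26 SD of change, or at most 0.37 raw SD for any non-negative correlation, against the 0.4 described as moderate. This rests on a paired t-test. The 60% criterion that the synopsis says must be demonstrated is tested and reported nowhere in section 11. A significant result would show a pre-post change, which a non-specific response alone could produce; the probabilities in step 3 illustrate this under assumed shifts and do not estimate it. The plan should be corrected, but neither its sample size nor its primary test is invalidated by this point.

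**What to change.** 1. **Section 6.1.** Replace the sentence with a statement that the primary test is against zero change, does not adjust for placebo response and does not require a moderate observed effect, and that a significant result shows a pre-post change in which placebo and treatment effects are summed. If a 40% versus 60% responder calculation was in fact used, describe it in section 11.2 in place of the LDQ effect-size account.
2. **Synopsis, sections 3.8 and 11.2.** Remove the statements that the 60% criterion compensates for placebo or demonstrates clinical efficacy. Use one wording and call it a descriptive target. Report the share improved with an exact 95% interval (36/60 would read 46.5% to 72.4%), with no comparison against the figure of up to 40%.
3. **Baseline.** Define improvement on the LDQ from one baseline at which it is actually collected. This means reconciling visit 1 (sections 4.2 and 5.1) with the run-in (synopsis, 3.8, 11.2), and the study schedule, which lists the LDQ at visits 1 and 3 only, with section 9.2, which says three times. A run-in LDQ should not be assumed to exist: section 9.3.1 has patients record daily symptoms in the app without naming the LDQ.
4. **Section 5.1.** Reconcile the wording on verifying efficacy with the section 6.1 statement that the design cannot evaluate it.

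The cost is wording changes and one descriptive analysis; if a visit 1 baseline is chosen, it needs no new data. The downside is a more modest claim, and the responder share will itself describe only a pre-post change.
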